## 1.3. Changes from Protocol

The following statistical analysis changes from the protocol will be implemented:

### 1.3.1. Validity of ABPM measurements

Section 10.7 of the protocol defines an ABPM measurement as valid based on the following six criteria:

- a. The time of the first study measurement is between 07:00 and 10:00.
- b. The duration, from the first study measurement to the last study measurement, is at least 25 h (1500 min).
- c. There are at least 21 study measurements recorded during the standard daytime period (09:00 to 21:00).
- d. There are at least 8 study measurements recorded during the standard night-time period (01:00 to 06:00).
- e. There are at least 35 study measurements recorded after the white-coat window.
- f. There are no more than 3 hours with a total measurement weight of less than 20 min and no more than 2 consecutive hours with total measurement weights each of less than 20 min.

For the efficacy analysis, the validity of ABPM measurements will instead be based on valid daytime measurements (i.e., bullet c), as the remainder of the period has no effect on the primary endpoint, which is average daytime (9:00 to 21:00) ambulatory systolic blood pressure (SBPday). Thus, all ABPM measurements with an assigned day validity of valid will be considered valid, regardless of the assigned night, 24h, overall, or other validities.

The impact of redefining a valid ABPM measurement based only on the validity of the daytime measurements (i.e., bullet c) is that the analyses of the secondary ABPM efficacy parameters [average 24-hour ambulatory systolic blood pressure (SBP24h) and DBP24h] and exploratory ABPM efficacy parameters [average night-time (01:00 to 06:00) ambulatory systolic blood pressure (SBPnight) and DBPnight] may include invalid measurements with respect to the 24-hour period (i.e., may not meet criterion d or e) or night-time period (i.e., may not meet criterion d), respectively. It is anticipated that this will be a very small number of cases and will not impact the secondary and exploratory efficacy conclusions drawn. Sensitivity analyses will be conducted to verify this point (see Section 1.3.3.1 below).

It should be noted that for establishing eligibility, the validity of the ABPM continued to be based on the definition of ABPM validity in the protocol. Thus, in order to be enrolled, subjects had to have a baseline ABPM that met all of the criteria above (a, b, c, d, e, and f).

Documentation of the individual validity criteria Dabl applied to assign overall, daytime, nighttime, 24h, and other ABPM validity flags is provided in “Note to File – Link of Individual Protocol-Specified ABPM Validity Criteria to Dabl Daytime, Nighttime, and 24h Validity Flags”, a copy of which is available in the Trial Master File.

### **1.3.2. Definition of Intent-to-Treat (ITT) and Modified Intent-to-Treat (mITT) populations**

The definition of the ITT population as stated in the protocol was at risk of losing randomized subjects and will be changed to remain faithful to the ITT principal. The ITT population will include all randomized subjects with a valid ABPM measurement at Baseline (according to the definition of validity described in Section 1.3.1 above). The protocol definition requires valid Baseline and valid follow-up ABPM measurements, either Day 6 or Day 13. This definition will instead be used for a mITT population, and the mITT population will be used for sensitivity analyses (see Section 1.3.3.2 below).

### **1.3.3. Sensitivity analyses**

#### **1.3.3.1. Sensitivity analysis for the validity of ABPM measurements**

The following sensitivity analyses will be performed to verify that redefining a valid ABPM measurement based only on the validity of the daytime measurements (see Section 1.3.1 above for further detail) will not impact the secondary and exploratory ABPM efficacy conclusions drawn:

1. ITT for SBP24h excluding SBP24h values that had an entry of valid for day validity and an entry of invalid for night or 24h validity (i.e., did not meet criterion d or e, respectively)
2. ITT for DBP24h excluding DBP24h values that had an entry of valid for day validity and an entry of invalid for night or 24h validity (i.e., did not meet criterion d or e, respectively)
3. ITT for SBPnight excluding SBPnight values that had an entry of valid for day validity and an entry of invalid for night validity (i.e., did not meet criterion d)
4. ITT for DBPnight excluding DBPnight values that had an entry of valid for day validity and an entry of invalid for night validity (i.e., did not meet criterion d)

#### **1.3.3.2. Sensitivity analysis of ITT versus mITT population**

A sensitivity analysis will be conducted to insure the change in definition of the ITT population (see Section 1.3.2 above) does not impact the study conclusions. A mITT population will be based on the definition originally presented as the ITT population in the protocol (valid Baseline and at least one valid follow-up ABPM measurement) and a second set of analyses will be conducted purely to demonstrate the definition does not have an impact on the primary and secondary efficacy analyses.

The following analyses will be conducted:

1. mITT for SBPday
2. mITT for SBP24h
3. mITT for DBP24h

#### **1.3.3.3. Sensitivity analysis of baseline effect**

To assess the impact of baseline, a further sensitivity analysis will be conducted on the primary endpoint (mean change of SBPday) using a regression model adjusted from Baseline on ITT, mITT, and per-protocol (PP) populations.

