	
as the predictive factor. There will be no covariate adjustments. Post-hoc comparisons for individual differences will use the Bonferroni Method.
 
$H_0: \Delta BW_1 = \Delta BW_2 = \Delta BW_3$
 
$H_1$: At least one difference.
 
Where ΔBW_1 is the reduction in body weight for subjects in arm 1
 
ΔBW_2 is the reduction in body weight for subjects in arm 2
 
ΔBW_3 is the reduction in body weight for subjects in arm 3
 
A two-sample t-test for superiority will be used for the secondary blood pressure efficacy analyses to test the one-sided hypotheses that treatment with amlodipine tablets (10 mg) and celecoxib capsules (200 mg) given together (arm 1) lowers SBP_{24h} to a greater degree than amlodipine tablets (10 mg) given alone (with matched celecoxib placebo) (arm 2).
 
$H_0: \Delta SBP_{24h,1} - \Delta SBP_{24h,2} = 0$
 
$H_1: \Delta SBP_{24h,1} - \Delta SBP_{24h,2} > 0$
 
Where $\Delta SBP_{24h,1}$ is the reduction in SBP_{24h} for subjects in arm 1
 
$\Delta SBP_{24h,2}$ is the reduction in SBP_{24h} for subjects in arm 2
 
For the next endpoint, SBP_{24h} will be replaced with DBP_{24h}.
 
For the creatinine clearance endpoint, a two-sample t-test for superiority will be used for the analysis to test the one-sided hypothesis that treatment with amlodipine tablets (10 mg) and celecoxib capsules (200 mg) given together (arm 1) improves creatinine clearance to a greater degree than amlodipine tablets (10 mg) given alone (with matched celecoxib placebo) (arm 2).

Statistical Methods for PK Drug-Drug Interaction Analysis:
	
Only subjects enrolled at Investigational Sites that have UV-shielded lights will participate in the PK blood collections.
 
Blood samples will be collected on Day 14, approximately 24 hours after receiving the final dose of study drugs. The plasma concentration of amlodipine will be determined by a validated liquid chromatography tandem mass spectroscopy (LC-MS/MS) method.
 
A t-test will compare the plasma concentration of amlodipine in those subjects who receive amlodipine tablets (10 mg) given alone (with matched celecoxib placebo) (arm 2) with those who receive amlodipine tablets (10 mg) and celecoxib capsules (200 mg) given together (arm 1).

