10.2.3 Primary Efficacy Endpoint Analysis

A two-sample t-test will be used to test the one-sided hypothesis that treatment with amlodipine tablets (10 mg) and celecoxib capsules (200 mg) given together (arm 1) is non-inferior to half of the effect achieved with the control treatment with amlodipine tablets (10 mg) given alone (with matched celecoxib placebo) (arm 2).

$$H_0: \Delta SBP_{day,1} - 0.5(\Delta SBP_{day,2}) \geq 0 \text{ mmHg}$$

$$H_1: \Delta SBP_{day,1} - 0.5(\Delta SBP_{day,2}) < 0 \text{ mmHg}$$

Where $\Delta SBP_{day,1}$ is the change, for subjects in arm 1, in the SBP_{day} from the baseline ABPM measurement ($SBP_{day,1,0}$) to the final ABPM measurement ($SBP_{day,1,14}$).

$$\Delta SBP_{day,1} = SBP_{day,1,0} - SBP_{day,1,14}.$$

$\Delta SBP_{day,2}$ is the change, for subjects in arm 2, in SBP_{day} from the baseline ABPM measurement ($SBP_{day,2,0}$) to the final ABPM measurement ($SBP_{day,2,14}$).

$$\Delta SBP_{day,2} = SBP_{day,2,0} - SBP_{day,2,14}.$$

Refer to Appendix H for further details regarding the efficacy analysis, and in particular the non-inferiority margin.

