#### **1.3.5. Definition of one-sided confidence interval (CI)**

For clarity, the non-inferiority trial will be based on comparing the change from baseline to end of study for the OE amlodipine besylate tablet and OE celecoxib capsule arm (treatment arm 1) minus 0.5 \* the OE amlodipine besylate tablet and matched placebo for OE celecoxib capsule arm (treatment arm 2) with 0. A one-sided 97.5% CI for  $\delta$  will be computed. This is consistent and equivalent with the hypothesis section of the protocol, which states that the primary efficacy endpoint will be that the lower limit of the 95% CI for SBPday reduction in treatment arm 1 will be at least 50% of the mean reduction in treatment arm 2. This statement is to clear up places in the protocol and SAP that conceptually state the comparison in less technical language.

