### 7.2. Covariates and Subgroups

All ANCOVA models will include the baseline value of the variable as a covariate and treatment group as fixed effect with no interaction term.

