### **7.7. Primary Efficacy Analysis**

The primary efficacy analysis is to establish the non-inferiority of amlodipine tablets (10 mg) and celecoxib capsules (200 mg) given together (arm 1) with half the effect achieved with amlodipine tablets (10 mg) given alone (celecoxib placebo) (arm 2).

Statistics are based on the change in BP from the baseline ABPM measurement (Day -1 to Day 0) to the post-dose ABPM measurement (Day 13 to Day 14 or if a LOCF is required Day 6 to Day 7), as this represents the efficacy of the treatment. As indicated below, the change will be Day 13 to Day 14 minus Baseline and so a reduction will be a negative number. Sensitivity analysis will compare the results for the ITT population with those of the PP dataset and an MMRM analysis, if possible. A sensitivity analysis will also compare the results with the mITT population.

The hypothesis test being conducted is as follows:

$$H_0: \Delta SBP_{day,1} - 0.5(\Delta SBP_{day,2}) \geq 0 \text{ mmHg}$$

$$H_1: \Delta SBP_{day,1} - 0.5(\Delta SBP_{day,2}) < 0 \text{ mmHg}$$

Where  $\Delta SBP_{day,1}$  is the change, for subjects in arm 1, in the  $SBP_{day}$  from the baseline ABPM measurement ( $SBP_{day,1,base}$ ) to the final ABPM measurement ( $SBP_{day,1,14}$ ).

$$\Delta SBP_{day,1} = SBP_{day,1,14} - SBP_{day,1,base}.$$

$\Delta SBP_{day,2}$  is the change, for subjects in arm 2, in  $SBP_{day}$  from the baseline ABPM measurement ( $SBP_{day,2,0}$ ) to the final ABPM measurement ( $SBP_{day,2,14}$ ).

$$\Delta SBP_{day,2} = SBP_{day,2,14} - SBP_{day,2,base}.$$

This makes the actual test statistic:

$$\delta = \Delta SBP_{day,1} - 0.5(\Delta SBP_{day,2})$$

A one-sided 97.5% CI for  $\delta$  will be computed. In addition, a two-sided non-inferiority t-test comparing  $\delta$  to 0 will provide an appropriate p-value. This p-value will be computing the probability of observing a value  $\geq 0$  from a normal distribution for  $\delta$ .

Refer to the protocol Appendix H for further details regarding the efficacy analysis, and in particular the non-inferiority margin.

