2. A two-sample t-test for superiority will be used to test the one-sided hypothesis that treatment with amlodipine tablets (10 mg) and celecoxib capsules (200 mg) given together (arm 1) lowers SBP24h to a greater degree than amlodipine tablets (10 mg) given alone (with matched celecoxib placebo) (arm 2).

$$H_0: \Delta SBP_{24h,1} - \Delta SBP_{24h,2} = 0$$

$$H_1: \Delta SBP_{24h,1} - \Delta SBP_{24h,2} > 0$$

Where  $\Delta SBP_{24h,1}$  is the change, for subjects in arm 1, in SBP24h from the baseline ABPM measurement to the post-treatment ABPM measurement.

$\Delta SBP_{24h,2}$  is the change, for subjects in arm 2, in SBP24h from the baseline ABPM measurement to the post-treatment ABPM measurement.

3. A two-sample t-test for superiority will be used to test the one-sided hypothesis that treatment with amlodipine tablets (10 mg) and celecoxib capsules (200 mg) given together (arm 1) lowers DBP24h to a greater degree than amlodipine tablets (10 mg) given alone (with matched celecoxib placebo) (arm 2).

$$H_0: \Delta DBP_{24h,1} - \Delta DBP_{24h,2} = 0$$

$$H_1: \Delta DBP_{24h,1} - \Delta DBP_{24h,2} > 0$$

Where  $\Delta DBP_{24h,1}$  is the change, for subjects in arm 1, in DBP24h from the baseline ABPM measurement to the post-treatment ABPM measurement.

$\Delta DBP_{24h,2}$  is the change, for subjects in arm 2, in DBP24h from the baseline ABPM measurement to the post-treatment ABPM measurement.

4. A two-sample t-test for superiority will be used to test the one-sided hypothesis that treatment with amlodipine tablets (10 mg) and celecoxib capsules (200 mg) given together (arm 1) improves creatinine clearance to a greater degree than amlodipine tablets (10 mg) given alone (with matched celecoxib placebo) (arm 2).

Note: an improvement in creatinine clearance is assumed to be an increase in creatinine clearance; therefore, a positive difference is an indication of improvement as shown in the following hypotheses.

$$H_0: \Delta CC_1 - \Delta CC_2 = 0$$

$$H_1: \Delta CC_1 - \Delta CC_2 > 0$$

Where  $\Delta CC_1$  is the change, for subjects in arm 1, in creatinine clearance from the baseline creatinine clearance to the post-treatment creatinine clearance.

$\Delta CC_2$  is the change, for subjects in arm 2, in creatinine clearance from the baseline creatinine clearance to the post-treatment creatinine clearance.

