### **Exploratory efficacy analyses**

Exploratory efficacy analyses will include two-sample t-tests to test one-side hypotheses of superiority for pairwise comparisons between treatment arms 1 and 2, 1 and 3, and 2 and 3 for DBPday, SBPnight and DBPnight.

Further, two-sample t-tests to test one-side hypotheses of superiority for pairwise comparisons between treatment arms 1 and 3 and 2 and 3 will be performed for SBPday, SBP24h, and DBP24h (the comparison of treatment arms 1 and 2 for these endpoints are covered separately under the respective primary and secondary efficacy analyses).

All exploratory efficacy comparisons will be based on the mean reduction in BP from the baseline (Day -1 to Day 0) ABPM measurement to the Day 13 to Day 14 ABPM measurement (or if a LOCF was required, the Day 6 to Day 7 ABPM measurement). The analyses will use the ITT data set including LOCF (and MMRM if possible) for subjects who were withdrawn from treatment early. Sensitivity analyses will be used to compare these results to those of the PP data set.

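### The efficacy tests on change from baseline are unadjusted although baseline is collected; the loss is precision only, and SBP24h, DBP24h and creatinine clearance have no baseline-adjusted analysis.

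*SAP*

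**What the plan says.** **Primary.** Protocol 10.2.3: "A two-sample t-test will be used to test the one-sided hypothesis that treatment with amlodipine tablets". SAP 1.3.5 says "the non-inferiority trial will be based on comparing the change from baseline to end of study", and SAP 7.7 defines delta as the mean change in arm 1 minus 0.5 times the mean change in arm 2, tested against 0 by a t-test with a one-sided 97.5% interval. Baseline is not in the test. The supporting analyses named in SAP 7.7 are "those of the PP dataset and an MMRM analysis, if possible"; the MMRM's covariates are not stated.

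**Secondary.** For SBP24h, DBP24h and creatinine clearance, SAP 7.8 uses the same form of words: "A two-sample t-test for superiority will be used to test the one-sided hypothesis that treatment with amlodipine tablets". Body weight is compared by ANOVA, and the protocol synopsis adds: "There will be no covariate adjustments".

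**Exploratory.** SAP 7.10: "Exploratory efficacy analyses will include two-sample t-tests to test one-side hypotheses of superiority".

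**Where baseline is used.** SAP 7.2: "All ANCOVA models will include the baseline value of the variable as a covariate and treatment group as fixed effect with no interaction term". The ANCOVA models in the SAP are all in SAP 7.9 (safety): body weight, clinic SBP and DBP, orthostatic blood pressures, serum creatinine and BUN. The one baseline-adjusted efficacy model is the SBPday regression in SAP 1.3.3.3 ("To assess the impact of baseline, a further sensitivity analysis will be conducted on the primary endpoint"), repeated in SAP 7.10, for the ITT, mITT and PP populations. Neither place mentions delta, the baseline value at which it is evaluated, or its standard error.

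**Availability.** Protocol section 3 requires review of the baseline ABPM before randomisation, and SAP 4.1 makes a valid baseline ABPM a condition of the ITT population.

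**The concern.** When baseline predicts the size of the change, leaving it out of the model leaves explainable variation in the error term. Here the covariate is already collected, and the SAP uses it for related variables. Clinic blood pressure is adjusted while ambulatory pressure, the official efficacy measure, is not. Body-weight change is tested unadjusted for efficacy and adjusted for safety. No reason is given for the difference.

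What is at stake is power, mainly for the superiority tests of arm 1 against arm 2. SAP 1.1 says the trial was meant to confirm the greater blood-pressure reduction with the combination, and in the hierarchy SBP24h must succeed before success can be claimed on DBP24h. A smaller matter is that the adjusted SBPday analysis is not fully defined for a contrast with weights 1 and -0.5.

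**Working it through.** **Inputs from the documents.** Previous study KIT-302-03-01 (Protocol Appendix H.1), reductions for amlodipine alone and for the combination:
- SBPday 8.8 (SD 8.1) and 10.6 (SD 9.2)
- SBPnight 6.4 (SD 11.4) and 10.5 (SD 10.6)
- DBPday 5.5 (SD 5.1) and 7.5 (SD 6.4)
- DBPnight 3.2 (SD 7.8) and 7.0 (SD 8.6)

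Planned size is 45 per active arm, entry SBPday above 135 and up to 169 mmHg, one-sided alpha 0.025 (SAP 3.1).

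**Assumed.** The correlation r between baseline and change, in absolute value, from 0 to 0.5. The amlodipine label (Protocol Appendix F, 12.2) says response rises with pretreatment elevation, which supports r above 0, but it quantifies this only for two diastolic bands. Baseline SD of SBPday: about 8 mmHg. The superiority tests are taken at one-sided 0.025.

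**The plan's own figures.** d = 10.6 - 0.5 x 8.8 = 6.2. Pooled SD = sqrt((8.1^2 + 9.2^2)/2) = 8.67, stated as 8.7. The sample-size formula gives 2 x ((1.960 + 0.842)/6.2)^2 x 8.7^2 = 30.9, so 31 per group. Appendix H.4 says 27, which the formula returns with s = 8.1 (26.8). That is a separate matter; the point here uses the final 45 per arm.

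**Variance of delta.**
- Unadjusted: 1.25 s^2/45. SE = 8.7 x sqrt(1.25/45) = 1.45; interval half-width = 1.987 x 1.45 = 2.88 mmHg.
- Adjusted, evaluated at the pooled baseline mean of arms 1 and 2: s^2(1 - r^2) x 1.25/45 + 0.25 b^2 s_x^2/90, where b is the baseline slope and s_x the baseline SD, so b^2 s_x^2 = r^2 s^2. The second term arises because the weights sum to 0.5 and the mean is estimated.
- Ratio = 1 - r^2 + 0.1 r^2 = 1 - 0.9 r^2, times about 1.01 for estimating the slope. For r = 0, 0.1, 0.2, 0.3, 0.4, 0.5 this is about +1%, 0%, -3%, -7%, -14%, -21% (simulation, baseline truncated to 135-169 mmHg).

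**Primary power, 45 per arm, SD 8.7.** If celecoxib adds nothing, d = 8.8 - 0.5 x 8.8 = 4.4.

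| d (mmHg) | unadjusted | r = 0.3 | r = 0.5 |
|---|---|---|---|
| 6.2 | about 99% | 99% or more | 99% or more |
| 4.4 | about 85% | 87-88% | 92% |

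At d = 4.4 and r of 0.2 or less the gain is at most about 1 point.

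**Type I error.** At the null boundary both the unadjusted test and the adjusted test with the extra variance term reject in 2.3% to 2.6% of simulated trials. Without that term the adjusted test rejects in about 2.7-2.8% at r = 0.5.

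**SBP24h, arm 1 against arm 2.** No 24-hour figures are given, so day and night are stand-ins (noncentral t).

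| stand-in | gap | SD | unadjusted | r = 0.3 | r = 0.5 |
|---|---|---|---|---|---|
| SBPday | 1.8 | 8.67 | 16% | 17% | 20% |
| SBPnight | 4.1 | 11.0 | 42% | 45% | 52% |

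**DBP24h.** SAP 1.1 says DBP24h and DBPnight reached significance in the previous study. That study had about 152 x 1.5/5 = 45.6 subjects per amlodipine arm. At 45 per arm its figures give two-sided p = 0.33, 0.08, 0.10 and 0.03 for SBPday, SBPnight, DBPday and DBPnight. SBPnight (one-sided 0.04) was not called significant, which points to a two-sided 5% criterion. A result just significant on that criterion, if it is the true effect, has about 50% power at one-sided 0.025. So unadjusted DBP24h power is about 50% or more. The DBPnight stand-in (gap 3.8, SD 8.21) gives 58%, rising to 62% at r = 0.3 and 70% at r = 0.5.

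Nothing can be computed for creatinine clearance or body weight.

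**Evaluation point.** With a common slope, the adjusted delta moves by 0.5 x r x 8.7/8 per mmHg of chosen baseline: 0.05, 0.16 and 0.27 mmHg at r = 0.1, 0.3 and 0.5. The two-arm and three-arm baseline means differ by about 0.3 mmHg (one SD), which moves delta by less than 0.1 mmHg.

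**The case against.** The case against is substantial. A t-test on change is valid in a randomised trial, so nothing prespecified is wrong. The gain depends on r, which the documents do not give. At r = 0.3 it is 2-3 points for the primary at d = 4.4, where power already exceeds the planned 80%, and 1-4 points for the superiority tests. Adjustment does not cure low SBP24h power. Adjusted analyses already exist for SBPday, and in the safety section for body weight, clinic pressure and serum creatinine, from which clearance is calculated. SAP 1.5 lists v4.0 as post-unblinding, so analyses added there cannot change any decision. All of this stands as a limit on the size of the point. It does not supply an adjusted analysis for SBP24h, DBP24h or clearance.

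Three stronger readings are tempting, and the documents do not support them:
- A reader might infer that the unadjusted tests are biased or inflate type I error. They do not; the boundary rejection rates are the same.
- A reader might take DBPday as the lower stand-in and infer DBP24h power of only 37%. DBPday was not significant in the previous study (p = 0.10 above) and DBP24h was, so that figure does not represent DBP24h.
- A reader might infer that the unstated evaluation point leaves the adjusted SBPday result arbitrary. Large shifts require evaluation at the edges of the entry range, and a reversed sign requires a baseline of 0 mmHg. The ordinary reading is the covariate mean, and plausible choices of mean differ by under 0.1 mmHg against a half-width of 2.9, in an analysis that decides nothing.

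**Conclusion.** The point holds as a loss of precision. The efficacy tests are valid but do not use a baseline that is already collected and that the SAP uses for its safety models. The primary conclusion is hardly affected at the planned difference and modestly at 4.4 mmHg. The gain matters more for SBP24h and DBP24h, where power is lower, and is noticeable mainly if r is 0.4 to 0.5. These sizes rest on the assumed r, on the previous study's effects holding, on day and night figures standing in for 24-hour ones, and on 45 per arm. The missing evaluation point is a minor gap in a sensitivity analysis. The change is worth making because it costs almost nothing, but no result is invalid without it.

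**What to change.** **In the protocol or a pre-unblinding SAP.** Analyse SBPday change and the secondary endpoints by ANCOVA on arm and baseline. For SBPday, take delta = LSmean1 - 0.5 x LSmean2 at the pooled baseline mean of arms 1 and 2, with a one-sided 97.5% interval and a variance equal to the usual contrast variance plus 0.25 b^2 s_x^2/N, where N is the number of subjects in that mean. Keep the unadjusted tests as sensitivity analyses.

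**In the post-unblinding v4.0.** Keep the t-tests as the decision tests. Add baseline-adjusted analyses of SBP24h, DBP24h and creatinine clearance, labelled post hoc. As a minor clarification, tie the regression in SAP 1.3.3.3 and 7.10 to delta as defined in SAP 1.3.5 and 7.7, evaluated at the pooled ITT baseline mean of arms 1 and 2 in all three populations, with the standard error above. Body weight needs nothing more, since SAP 7.9 already has its ANCOVA.

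**Cost.** Before unblinding: wording, one degree of freedom, about 1% more variance if r is near 0, and the extra variance term, which the unadjusted test does not need. After unblinding: one clarifying sentence and three post hoc analyses, with no new data.
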